#### SPONSOR PERSONNEL

### SYNOPSIS

Protocol Title:	An Open-Label, Single-Center, Randomized, 2-way Crossover Study to Evaluate the Relative Bioavailability of Varenicline Administered as OC-01 Nasal Spray as Compared to Varenicline Administered Orally as Chantix ®					
Protocol Number:	OPP-100					
Investigational Product:	OC-01 (varenicline) Nasal Spray					
Study Objectives:	Primary Objective: To assess the relative bioavailability of varenicline administered intranasally at its highest intended clinical strength compared to varenicline administered orally at its highest oral tablet strength.					
	Secondary Objective: To assess the clinical and laboratory safety of varenicline administered as a single dose orally and intranasally.					
	Overall Study Design					
Structure:	This is an open label, single dose, randomized, 2-way crossover study					
	Subjects will attend the unit for a screening assessment up to 28 days prior to the first dose.					
	Subjects who are eligible for the study will return to the unit for 2 in-unit treatment periods, each separated by a minimum of 14 days.					
	An End of Study visit will occur 7-14 days after the final dose.					
	The two study treatments are:					
	• Single oral dose of 1 mg varenicline (Chantix ® ).					
	
 
Intranasal dose of 0.12 mg OC-01 (varenicline)- delivered as a 50 μL (0.06 mg) spray into each nostril
 
					
	Treatment Period 1: Subjects will be admitted and will be randomly assigned to receive a single dose of varenicline either orally or intranasally. The administration dose will be delivered after an overnight fast by the subject.					
	PK samples will be collected pre-dose and in an intensive sampling regimen up to 120 hours post-dose to allow for the assay of varenicline.					
	Treatment Period 2: This period will be identical to Treatment Period 1 except that the administration of varenicline will be via the intranasal					

	
 
route for those subjects that previously received varenicline via the oral route. Those subjects that were previously administered oral varenicline during Treatment Period 1 will receive varenicline via the intranasal route.
 
End of Study Visit will occur 7-14 days after the final period's dose of varenicline when follow-up assessments will be performed.
 
					
Duration:	10 study visits over a period of approximately 60 days:					
	Screening: Day -28 to -2					
	Period 1: Day 1-3 (In-Unit Subjects will be confined in the Clinical Research Unit (CRU) from the morning of Day -1 until at least 48 hours post-dose (Day 3)); Day 4-6 (Out-Patient)					
	Period 2: Day 15-17 (In-Unit Subjects will be confined in the Clinical Research Unit (CRU) from the morning of Day 14 until at least 48 hours post-dose (Day 17)); Day 18-20 (Out-Patient)					
	End of Study: Day 27 + 7					
Control:	N/A					
Dosing Regimen:	Treatment A : Single oral dose of 1 mg of Chantix ® (varenicline) administered orally					
	Treatment B: Intranasal dose of 0.12 mg OC-01 (varenicline)- delivered as a 50 $\mu$ L (0.06 mg) spray into each nostril					
Collection Schedule:	Treatment Period 1 and Treatment Period 2:					
	All times are after study drug administration except for predose (time 0)					
	In-Unit Blood PK Sampling					
	Sample 1: Predose (time 0)					
	Sample 2: 5 minutes					
	Sample 3: 15 minutes					
	Sample 4: 30 minutes					
	Sample 5: 1 hour					
	Sample 6: 2 hours					

	Sample 7: 3 hours						
	Sample 8: 4 hours						
	Sample 9: 6 hours						
	Sample 10: 8 hours						
	Sample 11: 12 hours						
	Sample 12: 24 hours						
	Sample 13: 36 hours						
	Sample 14: 48 hours						
	Out-Patient Blood PK Sampling						
	Sample 15: 72 hours						
	Sample 16: 96 hours						
	Sample 17: 120 hours						
Sample Collection and Storage:	Blood samples (4 mL in K 2 EDTA tubes) are collected from an arm vein or catheter into Vacutainer tubes containing K 2 EDTA. Blood samples are mixed gently and maintained chilled until centrifuged within 2 hours of collection.						
	Plasma samples are separated into two equivalent aliquots and labeled appropriate with subject ID, site and nominal time point						
	Study Population Characteristics						
Number of Subjects:	Approximately 22 healthy volunteer subjects will be enrolled such that approximately 18 subjects complete the relevant PK assessments.						
Condition/Disease:	Healthy Volunteers						
Inclusion Criteria:	
 
Subjects must:
 
2. Have a body mass index between 18.0 and 32.0 kg/m^2, inclusive.
 
3. Be healthy as determined by a responsible and experienced physician based on a medical exploration including medical.
 
						

	history, physical examination, ECG and laboratory tests with no clinically significant findings.
	4. Have provided verbal and written informed consent.
	5. If a female of childbearing potential who is not using an acceptable means of birth control (acceptable methods of contraception include: hormonal – oral, implantable, injectable, or transdermal contraceptives, mechanical – spermicide in conjunction with a barrier such as a diaphragm or condom, IUD, or surgical sterilization of partner), have a negative urine pregnancy test at the Screening Visit.
Exclusion Criteria:	Subjects must NOT:
	1. Have had nasal or sinus surgery (including history of application of nasal cautery) or significant trauma to these areas.
	2. Have a vascularized polyp, severely deviated septum, chronic recurrent nosebleeds, or severe nasal airway obstruction as confirmed by intranasal examination at the Screening Visit.
	5. Any contraindication to varenicline according to the applicable label.
	
 
Have severe renal impairment (estimated creatinine clearance less than 30mL per minute).
 

	
 
Have current concomitant use of snuff, chewing tobacco, e- cigarettes or cigarettes/cigars during the study.
 

	9
	10. Have any condition or history that, in the opinion of the investigator, may interfere with study compliance, outcome

Page 6 of 44

Evaluation Criteria						
Pharmacokinetic Endpoints:	Varenicline plasma AUC 0-<math>\infty</math> , AUC 0-t , C max , T max , T <math>\frac{1}{2}</math> , K el					
Safety Measures:	Adverse events, clinical chemistry, hematology and urinalysis, vital signs assessments, physical examinations, ECGs and intranasal examinations.					
Statistical Methods:	Pharmacokinetics					

Page 8 of 44

Page 9 of 44

APPENDIX 5.				

### LIST OF ABBREVIATIONS

Term	Description				
AE	adverse event				
ALT	Alanine aminotransferase				
ANCOVA	analysis of covariance				
AST	aspartate aminotransferase				
AUC	area under the curve				
BID	two times a day				
BUN	blood urea nitrogen				
CAE ®	controlled adverse environment				
CFR	Code of Federal Regulations				
CI	confidence interval				
C max	maximum plasma concentration observed				
CRF	case report form				
ECG	electrocardiogram				
EDS	eye dryness score				
EDTA	ethylenediaminetetraacetic acid				
ENT	ear nose and throat				
DED	dry eye disease				
GGT	gamma-glutamyl transferase				
HIPAA	health Information Portability and Accountability Act				
IB	Investigator's Brochure				
ID	identification				
ICF	informed consent form				
ІСН	International Conference on Harmonisation				
IRB	Institutional Review Board				
ITT	intention to treat				
Kel	elimination rate constant				
Kg	kilograms				
logMAR	logarithm of the minimum angle of resolution				
LS	least square				
M 	meter square				

CONFIDENTIAL

Page 13 of 44

Term	Description				
MAD	mucosal atomization device				
MedDRA	Medical Dictionary for Regulatory Activities				
MI	multiple imputation				
μL	microliter				
mL	milliliter				
mm	millimeter				
nAChR	nicotinic acetylcholine receptor				
PCSA	potentially clinically significant abnormalities				
РК	pharmacokinetic				
РР	per protocol				
RBC	red blood cell count				
SAE	serious adverse event				
SAP	statistical analysis plan				
SGOT	serum glutamic oxalocaetic transaminase				
SGPT	serum glutamic-pyruvic transaminase				
SOC	standard of care				
TEAE	treatment-emergent adverse event				
T max	time to reach the maximum concentration observed				
US	United States				
WBC	white blood cell count				
WHO	World Health Organization				

OPP-100 Protocol Amendment #2

#### 1. INTRODUCTION

#### 2. STUDY OBJECTIVES

The primary objective is to assess the relative bioavailability of varenicline administered intranasally at its highest intended clinical strength compared to varenicline administered orally at its highest oral tablet strength.

The secondary objective is to assess the clinical and laboratory safety of varenicline administered orally and intranasally.

#### CONFIDENTIAL

Page 15 of 44

#### **3.** CLINICAL HYPOTHESES

No formal hypothesis testing will be performed.

### 4. **OVERALL STUDY DESIGN**

Protocol OPP-100 is a Phase 1, open-label, randomized, 2-way crossover study to evaluate the relative bioavailability of OC-01 (varenicline) Nasal Spray compared to varenicline administered orally as Chantix®. Approximately 22 healthy volunteer subjects between 18-65 years of age meeting all other study eligibility criteria will be randomized (Treatment Period 1) to receive an intranasal dose of 0.12 mg OC-01 (50  $\mu$ L spray of 0.06 mg into each nostril) or a single 1 mg oral dose of Chantix®. Both administrations will be delivered while subject is in an overnight fasted state. Subjects then will return at least 14 days later (Treatment Period 2) to receive the alternate dose of varenicline that was delivered at Treatment Period 1. Again, this delivery will be performed while subject is in an overnight fasted state.

Participants who terminate early during the application period will be asked to complete safety assessments (if the participants agree) prior to study exit. Participants who are terminated early from the study will not be replaced.

### 5. STUDY POPULATION

#### 5.1. Number of Subjects

Approximately 22 healthy volunteer participants will be enrolled at one site in the US. Subjects who are eligible for the study will return to the unit for two in-unit treatment periods, each separated by at least 14 days. The two study treatments are:

- Treatment A: Single oral dose of 1 mg varenicline (Chantix®) administered orally
- **Treatment B**: Intranasal dose of 0.12 mg OC-01 (varenicline)- delivered as a 50 µL (0.06 mg) spray into each nostril

### 5.2. Study Population Characteristics

All subjects must be between 18-65 years of age, inclusive of either gender, and of any race, and must meet all inclusion criteria and none of the exclusion criteria.

#### 5.3. Inclusion Criteria

Subjects must:

CONFIDENTIAL

Page 16 of 44

- 2. Have a body mass index between 18.0 and 32.0 kg/m^2, inclusive.
- Be healthy as determined by a responsible and experienced physician, based on a medical evaluation including medical history, physical examination, ECG and laboratory tests with no clinically significant findings.
- 4. Have provided verbal and written informed consent
- 5. If a female of childbearing potential who is not using an acceptable means of birth control (acceptable methods of contraception include: hormonal – oral, implantable, injectable, or transdermal contraceptives, mechanical – spermicide in conjunction with a barrier such as a diaphragm or condom, IUD, or surgical sterilization of partner), have a negative urine pregnancy test at the Screening Visit.

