#### 5.4. Exclusion Criteria

Subjects must not:

- 1. Have had nasal or sinus surgery (including history of application of nasal cautery) or significant trauma to these areas.
- 2. Have a vascularized polyp, severely deviated septum, chronic recurrent nosebleeds, or severe nasal airway obstruction as confirmed by intranasal examination at the Screening Visit.
- 5. Any contraindication to varenicline according to the applicable label.
- 6. Have severe renal impairment (estimated creatinine clearance less than 30mL per minute).
- Have current concomitant use of snuff, chewing tobacco, e-cigarettes or cigarettes/cigars during the study.

10. Have any condition or history that, in the opinion of the investigator, may interfere with study compliance, outcome measures, safety parameters, and/or the general medical condition of the subject.

12. Be a female who is pregnant, nursing an infant, or planning a pregnancy at the Screening Visit. Be a woman of childbearing potential who is not using an acceptable means of birth

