#### CONFIDENTIAL

Page 17 of 44

control; acceptable methods of contraception include: hormonal – oral, implantable, injectable, or transdermal contraceptives; mechanical – spermicide in conjunction with a barrier such as a diaphragm or condom; IUD; or surgical sterilization of partner.

13. Be currently enrolled in an investigational drug or device study or have used an investigational drug or device within 30 days or 90 for investigational biologics prior to the Screening Visit.

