#### Period 1 Check-In (Day -1)

- Serum pregnancy test (if applicable)
- Drug and Alcohol Screen
- Intranasal Examination
- Concomitant Medications

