#### APPENDIX 1. SCHEDULE OF VISITS AND MEASUREMENTS

Procedure	Screening	Period 1 Check-In	Period 1	Period 2 Check-In	Period 2	End of Study/Early Termination
	Day -28 to -2	Day -1	Days 1-6	Day 14	Days 15-20	Day 27 + 7 Days
Informed consent/HIPAA	X			2		
Demographics	Х			2		
Medical history	X					
Eligibility criteria	X					
Urine pregnancy test 	Х					Х
Serum pregnancy test 		Х		х		
Drug and Alcohol Screen	Х	X		х		
Physical Examination 	X					Х
12-lead ECG	Х					Х
Vital Signs 	X		Х		Х	X
Laboratory Samples (hematology, chemistry) 	х		$X^4$		X 	x
Urinalysis	X					X
Intranasal Examination	Х	Х		X		Х
PK Sample Collection 			Х		Х	
Randomization			Х			
Administer OC-01 (varenicline) Nasal Spray/Chantix®			Х		х	
Concomitant medications	X	Х	Х	X	X	X
AE Query	5		Х	X	X	X

 For females of childbearing potential

Weight and height collected at Screening Visit only

Vital signs including heart rate, respiratory rate and blood pressure will be obtained at Screening, prior to treatment administration at Periods 1 and 2, and 2 hours post treatment administration at Periods 1 and 2, and End of Study/Early Termination.

Clinical Chemistry to be performed at Screening, and 2 hours post treatment administration Periods 1 and 2, and End of Study/Early Termination. Hematology to be performed at Screening and End of Study/Early Termination.

PK samples collected at the following timepoints post treatment administration (predose, 5 minutes, 15 minutes, 30 minutes, 1 hour, 2 hours, 3 hours, 4 hours, 6 hours, 6 hours, 8 hours, 12 hours, 24 hours, 36 hours, 48 hours, 72 hours, 96 hours, 120 hours). Samples collected up to and including 48 hours will be performed In-Unit. Following the 48 hour sample collection subjects will be discharged and return for remaining samples on an Out-Patient basis.

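### Do inclusion 5 and exclusion 12 leave it open whether women not using contraception may enter, and whether enrolled women must test negative for pregnancy?

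*Protocol*

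**What the plan says.** Inclusion 5 in Protocol Section 5.3, repeated in the Synopsis, opens "If a female of childbearing potential who is not using an acceptable means of birth control" and then requires that she "have a negative urine pregnancy test at the Screening Visit".

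Exclusion 12 in Section 5.4 has two parts. The first bars anyone who would "Be a female who is pregnant, nursing an infant, or planning a pregnancy at the Screening Visit". The second bars anyone who would "Be a woman of childbearing potential who is not using an acceptable means of birth" control. It continues over the page break with the same list of methods as inclusion 5 and makes no exception for a negative test.

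Section 5.2 gives the rule for combining the lists: subjects "must meet all inclusion criteria and none of the exclusion criteria". Section 8.1.4 repeats it as the condition for final study entry.

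The schedule in Appendix 1 (also SAP Table 1) has a urine pregnancy test at Screening and End of Study, and a serum test at the Period 1 check-in (Day -1) and the Period 2 check-in (Day 14). Footnote 1 defines who is tested: "For females of childbearing potential", with no condition on contraception. The eligibility row is marked at Screening only. Section 8.7.2 lists pregnancy among the reasons for which a subject may be discontinued, and SAP Section 13.5 lists pregnancy results by subject.

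**The concern.** A test requirement placed only on women without contraception reads naturally as a conditional route into the study. Exclusion 12 then closes that route to exactly those women. If the exclusion governs, the negative-test criterion reaches nobody who can be enrolled, and the women who can be enrolled, those using contraception, have no negative-test line among the visible inclusion criteria.

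Timing adds to the worry. Exclusion 12 refers to the Screening Visit, and eligibility is ticked only there. Screening can be 28 days before the first dose and 42 days before the second. The serum tests at the two check-ins are not tied in words to randomization or dosing.

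At stake would be a participant-safety rule in healthy volunteers: one site reader might enrol a woman under Section 5.3 whom another would exclude under Section 5.4, and a positive check-in test might appear to meet no exclusion.

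**Working it through.** No power, alpha or sample-size figure is involved. The check is a truth table for women of childbearing potential, applying all inclusion and no exclusion criteria (Sections 5.2 and 8.1.4).

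| Contraception | Screening urine test | Inclusion 5 | Exclusion 12 | Eligible on these two criteria? |
|---|---|---|---|---|
| No | Negative | Met | Applies | No |
| No | Positive | Not met | Applies | No |
| Yes | Negative | Not triggered | Does not apply | Yes |
| Yes | Positive | Not triggered | Applies (pregnancy clause) | No |

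**Effect of inclusion 5.** It bears only on the first two rows, and exclusion 12 already bars both. Removing inclusion 5 changes no entry in the last column, so it is redundant. An inclusion criterion is a necessary condition, not a permission, so meeting it does not override an exclusion.

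**Are women on contraception covered?** Yes. Footnote 1 of Appendix 1 sends every female of childbearing potential to the screening urine test, and the pregnancy clause of exclusion 12 acts on a positive result (last row). The inclusion list lacks a test line for them, but the schedule and the exclusion together supply one.

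**Timing.** Under SAP Section 6.1 there is no Day 0, so Day -28 is 28 days before dosing on Day 1.
- Screening to first dose: 2 to 28 days.
- Screening to second dose, with the minimum 14-day interval: 2 + 14 = 16 to 28 + 14 = 42 days.
- Day -1 serum test to the Day 1 dose: 1 day.
- Day 14 serum test to the Day 15 dose: 15 - 14 = 1 day.

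The 28- and 42-day figures are right as arithmetic, but they measure from the screening test and pass over the serum tests. On the schedule, the latest pregnancy result is one day old at each dose.

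**Does a positive check-in test fall outside every rule?** Not on the visible text.
- In exclusion 12 the words about the Screening Visit can attach to planning a pregnancy alone, leaving the bar on pregnancy undated.
- Randomization is placed in Period 1, after the Day -1 check-in, and Section 8.1.5 randomizes only subjects who meet the eligibility requirements.
- Exclusion 10 covers any condition that, in the investigator's opinion, may affect safety parameters or the subject's medical condition.
- Section 5.5 allows withdrawal from treatment when safety is compromised, and Section 8.7.2 names pregnancy as a reason for discontinuation.

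**The case for a change.** The strongest case for acting is that both clauses stand in full in the current Amendment #2 text, concern participant safety, and could be aligned by wording alone, with no new visit or test. A site could still misread inclusion 5 as permission, or log eligibility deviations inconsistently. Section 8.7.2 is permissive, SAP Section 13.5 only lists results, and nothing visible says in terms what follows a positive Day -1 or Day 14 result.

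Part of this stands. Inclusion 5 does nothing as written, the group it names is not the group the schedule tests, and the consequence of a positive check-in test is left to be inferred.

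The rest does not. Opposite enrolment decisions cannot both be defended, because Sections 5.2 and 8.1.4 leave only one outcome for a woman without contraception. The claim that no exclusion would apply to a positive check-in test depends on one reading of exclusion 12. It also depends on an incomplete list: the public copy of Section 5.4 does not show exclusions 3, 4, 9, 11 and one of 7 and 8, and inclusion 1 is not visible either. Absence from the public copy is not absence from the plan.

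**Conclusion.** The overlap between inclusion 5 and exclusion 12 is a drafting slip without effect. The protocol's own combination rule reconciles the two. Aligning the wording would change eligibility for no woman, add or remove no test, and alter no endpoint, estimate or summary, so there is nothing to gain.

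The unstated consequence of a positive check-in test is a gap that an investigator would fill sensibly, with a serum result one day before each scheduled dose and several stated grounds for acting on it. What the clinical response should be is for the sponsor and investigator, and this review takes no position on it.

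The conclusion assumes that sites apply both lists together as Section 5.2 says, that the check-in tests are done as scheduled and read before dosing, and that the criteria not visible in the public copy do not contradict those that are. The number of women of childbearing potential among the approximately 22 subjects is not given, but the result does not depend on it.

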#### 5.4. Exclusion Criteria

Subjects must not:

- 1. Have had nasal or sinus surgery (including history of application of nasal cautery) or significant trauma to these areas.
- 2. Have a vascularized polyp, severely deviated septum, chronic recurrent nosebleeds, or severe nasal airway obstruction as confirmed by intranasal examination at the Screening Visit.
- 5. Any contraindication to varenicline according to the applicable label.
- 6. Have severe renal impairment (estimated creatinine clearance less than 30mL per minute).
- Have current concomitant use of snuff, chewing tobacco, e-cigarettes or cigarettes/cigars during the study.

10. Have any condition or history that, in the opinion of the investigator, may interfere with study compliance, outcome measures, safety parameters, and/or the general medical condition of the subject.

12. Be a female who is pregnant, nursing an infant, or planning a pregnancy at the Screening Visit. Be a woman of childbearing potential who is not using an acceptable means of birth

#### CONFIDENTIAL

Page 17 of 44

control; acceptable methods of contraception include: hormonal – oral, implantable, injectable, or transdermal contraceptives; mechanical – spermicide in conjunction with a barrier such as a diaphragm or condom; IUD; or surgical sterilization of partner.

13. Be currently enrolled in an investigational drug or device study or have used an investigational drug or device within 30 days or 90 for investigational biologics prior to the Screening Visit.

### 5.5. Withdrawal Criteria

If at any time during the study the Investigator determines that a subject's safety has been compromised, the subject may be withdrawn from treatment, but should attend the final follow up visit for safety evaluation.

Subjects may withdraw consent from the study at any time.

Sponsor and/or Investigator may discontinue any subject from study treatment for non- compliance or any valid medical reason during the course of the study (see Section 8.7.2 Discontinued Subjects).

